3.72 Secondary Outcomes

a) Sustained CDI resolution, defined as a lack of CDI recurrence 8 weeks after the last FMT treatment

Clinical status and biological samples will be taken to ensure that CDI has not recurred at 8 weeks

b) Adverse events

All serious adverse events will be recorded up to and including week 8 after the final FMT. A serious adverse event is any event which results in any of the following:

- Death
- Colonic perforation
- Proven infections related to FMT
- Subsequent hospitalization due to CDI within study period

c) Proportion of patients requiring colectomy

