3.3 Study Population

Patients admitted to hospital who fulfill the inclusion/exclusion criteria will be considered.

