4.0 Proposed Analysis

The primary outcome, defined as CDI resolution at week 2, will be analyzed using the per protocol approach for all patients. Adverse events will be tabulated in each predetermined outcome.

To measure the direct medical costs, the utilization of different health care services, including pharmaceuticals, physician services, Emergency Department visits, inpatient hospitalizations, and Intensive Care Unit time will be summed for each individual patient. In order to attempt to attach a dollar value to the resource utilization, CIHI's Resource Intensity Weights (RIW) will be used. The RIW methodology derives estimated resource utilization compared to an 'average typical hospital stay', the cost of which has been calculated for the Edmonton Zone in each fiscal year from 2010/11 through 2014/15. RIW values are calculated based on the patient's Comprehensive Ambulatory Classification System (CACS) group, age and based on the patient's Case Mix Group (CMG) code, age, and comorbidity level.

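### The closed four-item SAE list, and a synopsis window that opens only after the final FMT, allow serious harms in these inpatients to go unreported as SAEs

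*Protocol*

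**What the plan says.** The definition appears three times in the protocol: in the synopsis under study outcomes, in 2.0 secondary objective b, and in 3.72 b. Each time it takes the form "A serious adverse event is any event which results in any of the following", followed by four items. Besides death these are "Colonic perforation", "Proven infections related to FMT" and "Subsequent hospitalization due to CDI within study period". No general or catch-all item follows. Colectomy is a separate secondary outcome: "Proportion of patients requiring colectomy".

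On setting, 3.3 says "Patients admitted to hospital who fulfill the inclusion/exclusion criteria will be considered".

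On timing, 3.72 b says "All serious adverse events will be recorded up to and including week 8 after the final FMT", which gives an end and no beginning. Section 2.0 b is built the same way. The synopsis instead attaches the final FMT to the definition itself, so that the listed result must come after it.

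On reporting, 4.0 says "Adverse events will be tabulated in each predetermined outcome". Section 3.5 provides daily adverse event monitoring in hospital until 2 weeks after the final FMT, then weekly checks to week 8. Section 3.73 a collects ICU stay and length of stay as cost items. Section 5.0 appoints an independent DSMB.

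**The concern.** A safety outcome can only show what its definition admits. This list has three structural problems for patients with severe or fulminant CDI.

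- **Seriousness is tied to a few named results.** A patient who goes into shock, needs vasopressors or is moved to intensive care, and who survives without a listed result, has no SAE.
- **Causality is built into seriousness.** An infection counts only when its relation to FMT is proven. In a patient with severe colitis the source of a bloodstream infection may well stay uncertain, and an uncertain source means no SAE.
- **The admission item does not fit the setting.** It needs a new admission, and one due to CDI. Prolonging the current stay does not qualify, nor does readmission for another reason.

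Safety is a named purpose of the study and there is no concurrent arm, so nothing in the design would reveal an undercount. A low SAE count could be taken as evidence of tolerability when it partly reflects the definition.

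**Working it through.** The protocol states no SAE rate, and its sample size of 30 rests on expected patient volume (3.2). There is no figure of its own to reproduce, so the check is to run events through the text.

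**Step 1: which events qualify?**

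| Event | On the SAE list? | Recorded elsewhere in the protocol? |
|---|---|---|
| Death | Yes | – |
| Perforation, survived | Yes | – |
| Infection, FMT link proven | Yes | – |
| Infection, FMT link not proven, survived | No | No named outcome |
| Readmission for CDI | Yes | – |
| Readmission for another cause | No | No named harm outcome |
| Longer index stay | No | Length of stay, as a cost (3.73 a) |
| ICU transfer, survived | Only if it comes with a listed item | ICU stay, as a cost (3.73 a) |
| Shock or new vasopressor need, survived | Only if it comes with a listed item | Daily clinical monitoring (3.5) |
| New megacolon without perforation, survived | No | Only if it leads to colectomy (3.72 c) |
| Colectomy | No | Yes, own outcome (3.72 c) |

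Some non-fatal events in hospital are therefore counted, but whole classes are not.

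**Step 2: does another section bring the missing classes back?** Section 3.5 makes sure events are seen but does not make them SAEs. Section 4.0 promises tabulation by predetermined outcome, and the predetermined harm outcomes are the four items and colectomy. Section 5.0 does not say that the DSMB receives events outside the list. So no section repairs the gap.

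**Step 3: when does counting start?** Section 3.5 allows up to 4 cycles, each with FMT on days 1, 2 and 3, and then a closing enema that it calls final. The maximum is 4 × 3 + 1 = 13 administrations, so up to 12 can precede the final one. The synopsis wording can be read in two ways:

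- If the final FMT is the last one received, a listed event is lost whenever more FMT follows it. Death cannot be lost on this reading.
- If it is the closing enema of 3.5, every listed event before that enema is lost, and a patient who never reaches the enema has no window at all.

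Sections 2.0 b and 3.72 b impose neither restriction. The passages cannot all be applied as written.

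**Step 4: can the undercount be sized?** Only under assumptions. Let r be the risk of any serious event and s the share of affected patients whose event is on the list. The expected number of uncounted patients is 30 × r × (1 − s).

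- r = 10%, s = 75%: 30 × 0.10 × 0.25 = 0.75
- r = 50%, s = 25%: 30 × 0.50 × 0.75 = 11.25

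Neither r nor s is in the documents. A range of 0.75 to 11.25 patients shows only that the number is unknown.

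**Step 5: what would a clean table mean?** With 0 of 30 patients having a listed event, the exact two-sided 95% upper limit is 1 − 0.025^(1/30) = 11.6%. That limit covers listed events only and says nothing about unlisted ones.

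**The case against.** The strongest reply is that the trial does observe harm. Patients are assessed daily in hospital, including vital signs, vasopressor requirement and inflammatory markers, and then weekly. An independent DSMB sits over the trial. Perforation and proven FMT infection are non-fatal events that can occur in hospital and are listed. Colectomy, the likely result for patients who worsen and are referred for surgery, has its own outcome. The SAE objective is secondary and descriptive, in a 30-patient pilot without a safety threshold, and the primary outcome is unaffected. Detailed safety tables may stand in an SAP that is not shown.

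Most of this stands, and it limits the point to classification and promised reporting. It does not remove the point, because the definition of an SAE is a protocol matter and the protocol has fixed it, narrowly, in three places.

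A reader might infer more than the text supports, in three ways:

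- **That all non-fatal in-hospital events are omitted.** Perforation, proven FMT infection and colectomy show otherwise.
- **That most serious harms would never be counted.** This needs a listed share below 50%, and the documents give no rate. Choosing unlisted events and then assuming that some patients have them only returns the assumption.
- **That 4.0 forbids any other safety table.** It promises tabulation by predetermined outcome and does not exclude further tables.

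**Conclusion.** The point holds in limited form. As written, the SAE definition leaves out survived life-threatening events, prolongation of the index stay, readmission for causes other than CDI, and infections not proven to come from FMT. Such harms can be seen at the bedside and still not be reported as SAEs. Separately, the synopsis disagrees with 2.0 b and 3.72 b on when counting begins. On the synopsis wording, even a listed event during up to 4 treatment cycles can fall outside.

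The definition and the window conflict can be checked on the page and need no assumption. The number of patients affected cannot be stated. The conclusion assumes that the four items are meant as the complete definition, as their wording in all three places indicates, and that no unseen document overrides them. Because safety is a stated purpose and there is no control arm, the protocol text should be corrected.

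**What to change.** - **Definition.** In the synopsis, 2.0 b and 3.72 b, define an SAE by outcome regardless of cause: fatal, life-threatening, prolonging the current stay or leading to any new admission, causing lasting disability, or otherwise medically important.
- **Causality.** Record relatedness to FMT and to fidaxomicin as a separate field for each event.
- **Existing items.** Keep the four items as events of special interest, and keep colectomy as its own outcome.
- **Window.** Reconcile the three passages into one collection period, starting at first study treatment and running to week 8 after the final FMT. State what the final FMT means for a patient who stops early.
- **Analysis.** In 4.0, tabulate all SAEs as well as the four items.

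The cost is an amendment, more SAE forms in a very sick population, and a safety table that will look less favourable. No extra visits are needed, since the daily and weekly monitoring in 3.5 already provides the contact.

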Study Purpose	To determine the safety and efficacy of serial FMT and fidaxomicin in the treatment of severe or fulminant CDI
Study Design	Prospective, open label, multi-center study
Study Population	Patients with severe or fulminant CDI
Sample Size	30
Dosing	
Each cycle consists of:
 
 1. Serial FMT: 720 cc (1st treatment), 360 cc (2nd Rx), and 180 cc (3rd Rx) of fecal slurry 2. Fidaxomicin: 200 mg oral BID x7-10 days
Masking	None
Study Outcomes	
Primary outcomes
 
CDI resolution, defined as < 3 unformed bowel movements/ 24 hrs or a return to baseline bowel habit, 2 weeks after the last FMT treatment
 
Secondary outcomes
 
 1. Sustained CDI resolution, defined as a lack of CDI recurrence 8 weeks after the last FMT treatment 2. All serious adverse events up to and including week 8. A serious adverse event is any event which results in any of the following after the final FMT: 
 a. Death b. Colonic perforation c. Proven infection related to FMT d. Subsequent hospitalization due to CDI within study period 3. Need for colectomy

	
Exploratory outcomes
 
 1. All direct medical costs for CDI treatment 2. Changes in microbial composition, metabolomics and host immune response after treatment
Inclusion Criteria	
 1. Age > 18 years with severe¹ or fulminant² CDI, without an adequate response to metronidazole IV 500 mg q8H and vancomycin 500 mg PO q6h for at least 2 days or after a single Fecal Microbiota Transplant (FMT). An adequate response is defined as a decrease in stool frequency or inflammatory markers (WBC or C reactive protein) by at least 10% over 48 hours 2. Those with ability to provide informed consent or an alternative decision maker providing consent 
¹- Severe CDI defined as WBC > 15,000 cells/mm³ or serum creatinine level >1.5mg/dL or 1.5x premorbid level ²- Fulminant CDI defined as having any of the following attributable to CDI: Hypotension or shock, ileus, megacolon. An abdominal CT scan should be strongly considered to rule out perforation

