2.0 Objectives

Primary Objectives: To determine the clinical efficacy of combined serial FMT and Fidaxomicin in severe or fulminant CDI 2 weeks after the last FMT

Secondary Objectives:

- a) To determine sustained CDI resolution, defined as a lack of CDI recurrence 8 weeks after the last FMT treatment
- b) To describe serious adverse events up to and including week 8 after the final FMT. A serious adverse event is any event which results in any of the following:
 - i) Death
 - ii) Colonic perforation
 - iii) Proven infection related to FMT
 - iv) Subsequent hospitalization due to CDI within study period
- c) To determine colectomy rate in this patient population

Exploratory Objectives:

- a) All direct Medical costs for CDI treatment
- b) Changes in microbial composition, metabolomics and host immune response after combined serial FMT plus fidaxomicin

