3.32 Exclusion Criteria

- Those with bowel perforation
- Those taking chemotherapy or radiation treatment with absolute neutrophil count of < 1000 cells/mm3
- Those with colostomy or ileostomy or colonic strictures
- Those with subtotal colectomy or planning to have a colectomy
- Those with significant ileus

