3.5 Intervention and follow up

Patients who fulfill inclusion and exclusion criteria will be screened. Once consent has been obtained, metronidazole and vancomycin will be discontinued and 2L of Golytely will be administered the night prior to FMT. Each participant will undergo a large volume enema of 720cc delivered FMT on day 1, consisting of 200g of donor stool followed by two more days of small volume FMT enema on day 2 (360 cc) and day 3 (180 cc). This constitutes as cycle 1. In the event that a colonoscopy is indicated to rule out other pathology, then the scheduled enema can be delivered at the time of colonoscopy. On day 1, the patient will also start a 7-10 day course of fidaxomicin, as long as no clinical deterioration or complication such as bowel perforation has occurred. Following the first cycle of FMT treatment and fidaxomicin, careful clinical monitoring including vitals, requirement for vasopressors (if applicable), abdominal pain and distension, stool frequency and inflammatory markers including white blood cell (WBC) and C reactive protein (CRP) will be performed daily (Figure 3.0). If the patient has improvement in clinical parameters and inflammatory markers, and has reached a plateau without further changes over 24-48 hours after the first cycle, a second cycle of enema delivery of FMT will be administered. The FMT and fidaxomicin combined cycles will continue until clinical resolution of diarrhea and/or return of inflammatory markers to baseline prior to CDI. At that point, a final FMT 180cc enema will be administered. The maximal number of cycles is 4. At any time when a patient's conditions worsens, the study team will refer patient for surgery.

Each patient will receive FMT from a single donor with multiple collections obtained over time.

Baseline characteristics including age, sex, duration and response to CDI therapy, medical history (including inflammatory bowel disease, irritable bowel syndrome, baseline bowel habit, bowel resection, chemotherapy or radiation, number of CDI in the previous 12 months) and medication use will be collected. Blood work including CBC, electrolytes, creatinine, ALT, ALP, albumin, CRP, INR, HIV, and viral hepatitis serology will be drawn at screening visit (Figure 4.0). In addition, baseline collection of blood, and stool samples will be collected and

biobanked. Repeat stool and blood samples will be collected after each cycle of treatment, and again at week 1, 2, 4 and 8 after the final FMT.

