3.6 Subject Withdraw or Termination

Subjects will be discontinued from the trial in the following situations:

- Withdrawal of consent. The subject is free to withdraw from the trial without prejudice to further medical care
- Need for urgent colectomy

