3.7 Outcome Measures

3.71 Primary Outcome

CDI resolution, defined as < 3 unformed bowel movements/ 24 hrs or a return to baseline bowel habit, 2 weeks after the last FMT treatment

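### Worsening patients are referred for unspecified surgery, but only colectomy is named in the outcomes and discontinuation rule, and no clause makes surgery a failure of the primary outcome

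*Protocol*

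**What the plan says.** Section 3.5 gives the action on deterioration: "At any time when a patient's conditions worsens, the study team will refer patient for surgery". It does not name or limit the operation.

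The surgical outcome is worded as colectomy in three places:
- Synopsis: "Need for colectomy".
- Section 2.0: "To determine colectomy rate in this patient population".
- Section 3.72(c): "Proportion of patients requiring colectomy".

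Section 3.6 lists two reasons for discontinuing a subject: withdrawal of consent and "Need for urgent colectomy". The serious adverse event list in section 3.72(b) has four items (death, colonic perforation, proven infection from FMT, later hospitalization for CDI) and none is surgery.

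The primary outcome in section 3.71 is "CDI resolution, defined as < 3 unformed bowel movements/ 24 hrs or a return to baseline bowel habit, 2 weeks after the last FMT treatment". Section 4.0 analyses it by a per-protocol approach and does not describe which patients that set contains.

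**The concern.** Referral for surgery on worsening is the protocol's own marker that study treatment has not worked. One would expect it to lead to a defined place in the outcomes. Instead, the trigger in 3.5 is wider than the event counted in 3.72(c) and 3.6, and the primary outcome does not mention surgery at all.

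Two kinds of surgical patient are then left without a clear classification for the primary outcome. At stake is the resolution rate in a single-arm, open-label study of 30, where one patient is 3.3 points and no control group would share the same error.

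**Working it through.** The sample size of 30 is based on patient volume, so there is no power or error-rate figure to reproduce. The check is a tracing of definitions, followed by arithmetic for scale.

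**Step 1. Follow each surgical patient through the text.**

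| Question | Operation other than colectomy | Urgent colectomy |
|---|---|---|
| Within the 3.5 referral? | Yes, as worded | Yes |
| Counted in 3.72(c)? | No | Yes |
| Discontinued under 3.6? | No | Yes |
| On the serious adverse event list for the operation itself? | No | No |
| Declared not resolved in 3.71? | No | No |

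The first patient stays on study. The primary assessment is timed from the last FMT, so it can fall after the operation, and only stool count or bowel habit is then consulted. The second patient is discontinued. Nothing says whether that patient is scored as a failure, scored on stools or left out of the per-protocol set.

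**Step 2. Size if a surgical failure is scored as resolved.** Inputs: n = 30 (synopsis and section 3.2) and k misclassified patients (assumed). The shift is k/30, so 3.3, 6.7 and 10.0 points for k = 1, 2 and 3. Suppose, purely as an illustration, that 24 of 30 are truly resolved. Exact (Clopper-Pearson) 95% intervals:

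- k = 0: 24/30 = 80.0% (61.4 to 92.3)
- k = 1: 25/30 = 83.3% (65.3 to 94.4)
- k = 2: 26/30 = 86.7% (69.3 to 96.2)
- k = 3: 27/30 = 90.0% (73.5 to 97.9)

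**Step 3. Size if a surgical failure leaves the denominator.** With the same 24 resolved and k failures dropped, the rate is 24/(30 − k):

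- k = 1: 24/29 = 82.8%, up 2.8 points
- k = 2: 24/28 = 85.7%, up 5.7 points
- k = 3: 24/27 = 88.9%, up 8.9 points

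Both routes push the rate the same way and by similar amounts.

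**Step 4. The surgical outcome.** Each operation other than colectomy adds 1/30 = 3.3 points to an any-surgery rate and nothing to 3.72(c). With one such patient and no colectomy, 3.72(c) reports 0/30 (0 to 11.6%) while the any-surgery rate is 1/30 = 3.3% (0.1 to 17.2%).

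**Step 5. How likely is at least one case?** The protocol gives no frequency. Under an assumed per-patient probability p, the chance of one or more in 30 is 1 − (1 − p)^30: 45.5% for p = 2%, 78.5% for p = 5% and 95.8% for p = 10%.

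**The case against.** The best reply is that surgery in 3.5 simply means colectomy. The Introduction presents colectomy as the only alternative in severe or fulminant disease, and the pilot data in Figure 2.0 count success as colectomy avoided. No other operation for CDI is mentioned anywhere. On that reading 3.5, 3.6 and 3.72(c) agree. This has weight, but it is inferred from background text. Section 3.5 does not say it, and even if it were granted, 3.71 would still not say how a colectomy patient is scored.

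A reader might go further and infer that a patient given a diverting stoma will be recorded as resolved. The documents do not support that. They never describe a stoma as a treatment on study. The exclusion "Those with colostomy or ileostomy or colonic strictures" concerns anatomy at entry, not operations done later. The primary definition does not say how stoma output would be counted, and the per-protocol approach might remove such a patient rather than score a success.

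A reader might also infer that the colectomy rate is biased. It is not: an outcome defined as colectomy that counts colectomies is measured correctly. It is only narrower than the referral rule.

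Three further replies stand in part. Operations would not go unrecorded, since procedures are drawn from an administrative database (section 3.73), but that is for costs. The intervals in the illustration overlap heavily and no decision threshold depends on the rate. A SAP may define the per-protocol set, but one that counted other surgery under 3.72(c) would be changing an outcome the protocol has already worded.

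**Conclusion.** The mismatch in wording is real, and so is the absence of a surgery clause in the primary outcome. As written, a surgical failure can meet the stool criterion or leave the denominator, and either raises the resolution rate. The effect is 1/30 = 3.3 points for each patient wrongly scored as resolved, and about 3 points for each one dropped when 24 of 30 resolve.

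The total size is unknown. It rests on assumed counts, because the protocol gives no frequency for surgery other than colectomy, and the authors may have meant colectomy throughout. What is established is an ambiguity that can favour the treatment, not a demonstrated bias. It is a modest point, worth correcting because the correction is cheap.

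**What to change.** 1. In section 3.71, add that a patient who has any surgery for CDI or its complications before the 2-week assessment is counted as not resolved, whatever the stool count, and stays in the denominator.
2. Reconcile surgery in 3.5 with colectomy in 3.6, 3.72(c), 2.0 and the synopsis. For the outcome, report any surgery for CDI or its complications, with colectomy shown as a component so that the present figure is kept.
3. Record the type and date of each operation prospectively on the case report form.

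The cost is a few lines of wording and one form entry. The reported resolution and surgical rates may be slightly less favourable. The change concerns only how outcomes are counted and alters no clinical rule. When 3.5 and 3.6 are reconciled, which operations they should cover is for the investigators to state.

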3.73 Exploratory Outcomes

a) Costs for CDI Treatment

Direct Medical costs for CDI treatment will be obtained from administrative database to include length of hospital stay, procedures and tests performed, ICU stay and medication use.

b) Stool microbial composition analysis by metagenomics

Stool samples will be subjected to physical disruption using a bead-beating kit and microbial DNA extracted using the Qiagen QIAamp DNA stool kit and stored at -20°C. DNA will be used as input for the Illumina Nextera® XT DNA Sample Preparation Kit to construct indexed paired-end DNA libraries. The pooled and indexed library set will be denatured and sequenced on an Illumina MiSeq.

Whole-genome shotgun sequencing will be performed and taxonomic classification of reads from each library will be conducted with Kraken. The database used consisted of all bacteria, archaea, viruses, fungi, and protozoa full-length genomes from NCBI RefSeq, the human genome assembly GRCh38, and reference bacterial assemblies from the Human Microbiome Project. Read assignments were filtered with Kraken-filter using a threshold of 10%.

c) Stool Metabolomics analysis

Stool samples will be lyophilized for 24 hours using a VirTis Benchtop BTP 8ZL freeze dryer (BPS, UK). Dried samples will be weighed, and bile acids extracted using a 2:1:1 (vol) mixture of water, acetonitrile and 2-propanol in a Biospec bead beater with 1.0 mm Zirconia beads. Following centrifugation (16,000 x g, 20 minutes) the supernatant will be filtered using 0.45 µm microcentrifuge filters (Costar, Corning). Quality control (QC) samples will be prepared using equal parts of the fecal filtrates. QC samples will be used as an assay performance monitor, and as a proxy to remove features with high variation. QC samples will also be spiked with mixtures of bile acid standards (55 bile acid standards including 36 non-conjugated, 12 conjugated with taurine, seven conjugated with glycine (Steraloids, Newport, RI, USA)) and will be analyzed along with the stool samples to determine the chromatographic retention times of bile acids and to aid in metabolite identification.

Bile acid analysis of fecal extracts will be performed using ACQUITY UPLC (Waters Ltd, Elstree, UK) coupled to a Xevo G2 Q-ToF mass spectrometer equipped with an electrospray ionization source operating in negative ion mode (ESI-), using the method described by Sarafian and colleagues. Waters raw data files will be converted to NetCDF format and data will be extracted using XCMS (v1.50) package with R (v3.1.1) software. Probabilistic quotient normalisation⁶ will be used to correct for dilution effects and chromatographic features with coefficient of variation higher than 30% in the QC samples will be excluded from further analysis. The relative intensities of the features will be corrected to the dry weight of the fecal samples.

d) Blood Immunological profiling

Immunophenotypic analysis of peripheral immune cell populations through peripheral blood mononuclear cells (PBMCs) that will be isolated from buffy coats and stained with optimized combinations of fluorochrome-conjugated mAbs. Frequencies of T- and B-regulatory cells, as well as Th1, Th2 and Th17 populations will be ascertained using established flow cytometric antibody panels and isotype controls. Relevant signature cytokines and transcription factors will

also be included in an already established 9-colour FACS panel. We will also examine effector and memory B and T cell populations, in addition to plasma and dendritic cell populations plus their relevant signature cytokines and transcription factors (all pending sufficient availability of cells).

